Study Rationale	Adolescent alcohol exposure is associated with heightened automatic responses to stimuli that impede execution of goal-directed actions, and such behavioral inflexibility is a risk factor for alcohol and other substance use disorders. In this pilot study, we aim to determine the feasibility of delivering a 4-week online training of Koru mindfulness to freshman college students, in addition to a pre- and post-visit. Mindfulness meditation is known to reduce automatic responses to stimuli; however, it's unknown whether mindfulness training can increase behavioral flexibility in emerging adults with adolescent alcohol exposure. Young college adults experience demanding academic and social schedules that challenge maintenance of healthy behaviors while learning to adapt to emerging adulthood. Mindfulness training is one strategy to support healthy outcomes that persist despite inevitable stressors.
Study Objective(s)	
Primary
 
 • To determine the feasibility of subject recruitment, participant retention, visit attendance, and study design among freshman college students. 
Secondary
 
 • To assess participant satisfaction with study procedures.
Test Article(s) (If Applicable)	Koru Mindfulness Training
Study Design	This is a parallel assignment randomized controlled trial feasibility study. The two-armed study has the mindfulness meditation intervention and the control groups running parallel to one another. Participants are blinded to condition.
Subject Population key criteria for Inclusion and Exclusion:	
Inclusion Criteria
 
 • College enrolled first-year students aged 18-19 years old • Internet access to enable online training • Fluent English speaker (\leq age 7) • ≥ 4 lifetime binge drinking episodes • Meditation-naïve 
Exclusion Criteria
 
 • Subjects with known neurological, psychiatric, or systemic disease • Subjects with any type of motor or visual disturbance that may interfere with performing the cognitive task • Subjects using psychoactive drugs (aside from moderate caffeine or alcohol) or medications • Subjects with a known history of any substance use disorder (not including alcohol or nicotine) or desire to seek treatment for excess substance use
Number Of Subjects	18

Study Duration	
 • Each subject will undergo 4 weeks of intervention or control group training, a pre- and post-training visit, and a 1-month follow-up. • The entire study is expected to last 3 months.
Study Phases	(1) Subjects screened for eligibility and obtaining consent;
Screening	(2) Cognitive task performance, blood sample collection, surveys;
Study Treatment	(3) Four weeks of virtual training in Koru mindfulness or an age- and time-matched comparison group;
Follow-Up	(4) One-month follow up online surveys
Efficacy Evaluations	
 • Mean number of visits attended by participants and total number of journal entries.
Pharmacokinetic Evaluations	N/A
Safety Evaluations	Self-report measures of anxiety, depression, and stress will be evaluated at the beginning of each visit to determine any changes that could be in result of the intervention.
Statistical And Analytic Plan	
 • To assess the primary objective (feasibility) of the study, the primary outcome will be the count of participants in each of the 6 visits, and the number of surveys that are completed at the 1-month follow-up contact. • To assess the secondary objective (participant compliance), the secondary outcome will be measured by total journal entries submitted during the 4 weeks of intervention training.
DATA AND SAFETY MONITORING PLAN	The Co-Investigators will review participants' experiences with study procedures on a weekly basis. Meditation practice may elicit discomfort if traumatic memories resurface or the participant is experiencing high stress. The Koru teacher is trained in trauma-sensitive mindfulness and has implemented this awareness in the design of the visits. Nonetheless, the teacher will regularly check in with students to address any concerns.

BACKGROUND AND RATIONALE

1.1 Introduction

Lifetime risk for developing an alcohol use disorder increases with earlier onset of alcohol consumption [1-3]. This risk may reflect a tendency for escalated alcohol intake among youth due to immature executive control, leading to more frequent binge drinking, which is associated with more alcohol-related problems [4, 5]. Binge drinking is associated with deficits in behavioral flexibility [6, 7], which may suggest impaired control networks that contribute to automatic behavior [8]. Individuals with an alcohol or substance use disorder (A/SUD) exhibit attentional bias toward drug- or alcohol-related stimuli that have attained salience through consistent use [9-13]. Reward history increases attention towards non-drug stimuli, even among individuals with no lifetime A/SUD [14, 15]. Our preliminary data, from a nationally representative US adult sample using data collected via Prolific, found that a questionnaire measure of mindfulness moderates the relationship between alcohol misuse and attention to reward. Given evidence that heavy alcohol drinking impairs behavioral flexibility [6, 16], which in turn promotes escalating intake [17], insight into the relationship between mindfulness and behavioral flexibility could inspire new strategies to prevent alcohol and substance use disorders in people at elevated risk.

1.2 Name and Description of Investigational Product or Intervention

Koru Mindfulness (KM) Intervention Training

The Koru Basic curriculum [18] will consist of four weekly interactive 75-minute classes delivered online through Zoom. Each class will consist of an overview of 2-3 skills, group practice of the skills, and group reflection. Class size will be limited to 9 participants. Participants will have their video off and will have their own unique identifier (instead of identification by name). Participants will be instructed to practice a skill for 10 minutes/day and log their reflection on that practice using the Koru phone application.

Navigating College (NC) Control Group Training

The control group will consist of four weekly 75-minute classes delivered online through Zoom. Each class will consist of lecture and group discussions on topics related to navigating college [19]. Participants will be instructed to journal about learned information and skills for 10 minutes/day.

1.3 Non-Clinical and Clinical Study Findings

Potential benefits of this study include learning skills that may help the participant navigate their college experience with more ease. Additionally, participants in the KM intervention may experience decreased stress, anxiety, and sleep problems [18].

Answering the surveys may make the subjects uncomfortable and could cause emotional distress or embarrassment. Completing questionnaires and participating in computerized tasks may make subjects anxious or uncomfortable. Participants will be asked questions regarding use of illegal alcohol consumption (\leq age 21), use of illegal substances, and involvement in activities such as driving while under the influence of drugs and/or alcohol. To minimize this risk, participants may choose not to answer any question and they may terminate participation at any time during all tasks. Participant's data will only be identified using an ID assigned to them at the beginning of the study. Any paperwork that includes participants' names or other personal information will be kept separate from study documents with their ID number and will be stored in a locked file cabinet in the locked lab. All data will be archived without personal identifiers, using only ID numbers.

In 10 years of testing participants at UNC, including a study that recruited alcoholics (unlike this study), we have experienced a single instance of an acutely intoxicated participant arriving for a study, and no instances of participants in acute withdrawal. Therefore this scenario is highly unlikely. However, in the event that a participant arrives for a session intoxicated, we will help them arrange a ride home. If intoxication or withdrawal symptoms are severe, study personnel will escort participants to the UNC emergency room.

There are no risks for injury expected to occur with virtual discussion and training of mindfulness, meditation or college skills. Potential risks include boredom, fatigue, or discomfort with spending additional time on the computer, aside from schoolwork. Additional discomfort may arise during mindfulness practice for subjects who have previously experienced trauma or are currently experiencing high stress. Participants will be observed for any obvious discomfort and followed up with by the mindfulness teacher with trauma resources if necessary.

Rare: A participant's personal information could be linked with their study data. To minimize this risk, no one outside of the research team will have access to participants' data. Participants' data will only be identified in all computer analyses with their ID numbers. Any paperwork that includes participants' names or other personal information will be stored in a locked file cabinet in the locked lab. All data will be archived without personal identifiers, using only ID numbers.

Potential minor risks and discomforts are associated with cognitive testing. Although it is hoped that subjects will complete the study, subjects may stop participation at any time during the cognitive testing.

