4.2 Intervention procedures (by visits)

See Figure 1 for overview of study visits.

Visit 1

- Written consent, MINI interview [25], urine drug screen and breathalyzer alcohol test, C-reactive protein (CRP) assay, Reward-AB task

Visits 2-5

- Randomization to either the Koru Mindfulness (KM) intervention or the Navigating College (NC) control group.
- Each training visit will consist of the following:
 - Surveys completed online through REDCap.
 - 75 minutes of instructor-led discussion
 - Breakout sessions for participants to share their thoughts and experiences in response to instructor's prompt.

Navigating College (NC) Control Group Training

Topics discussed during each training visit include: habits, roommate issues, homesickness, the internet (week 1); strategies when sinking, study skills, getting involved, habit formation (week 2); HALT, gateway habit (week 3); and academic success tips, taking notes, and procrastination (week 4).

Koru Mindfulness (KM) Intervention Training

Topics discussed during each training visit include: belly breathing, dynamic breathing, body scan (week 1); walking meditation, gatha (week 2); guided imagery, labeling thoughts (week 3); eating meditation, and labeling feelings (week 4).

Daily Logging of Skills

Participants in the CG intervention will be asked to journal by hand or via Qualtrics every day for ≥ 10 minutes, on anything related to the topics learned during that week's training visit. Participants in the KM intervention will

be asked to practice every day for ≥ 10 minutes any mindfulness or meditation skill previously learned during training visits, in addition to logging their practice and reflection using the Koru application.

Visit 6

- Similar to visit 1, without repeating the MINI interview.

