8.1 Administration for Training Groups

After Visit 1, participants will be randomized to either the intervention or control group using a randomized number computer generator (e.g., 01-18 assigned to mindfulness meditation group). The NC and KM training instructor will be blinded to the group each participant is randomly assigned to, and participants will be assigned a unique ID to put as their name for their Zoom profile and on questionnaires. This number will be given (and recorded) by a research assistant. During training visits, all videos (except the instructor's) will be turned off.

SAFETY MANAGEMENT

We do not anticipate participant safety to be an issue in this study. Proposed procedures do pose a risk of harm if safety protocols are not followed carefully. To ensure participant safety, all participants will be thoroughly screened by trained personnel for the presence of conditions that could pose a threat to the subject. All research personnel will be trained in blood collection by finger prick. Daily practice logs will give participants a safe space to share any discomfort experienced during training. If participants in the KM group are experiencing extreme discomfort during weeks when visits 2-6 take place, due to resurfacing of traumatic experiences, subjects will be withdrawn from the study and given resources to alleviate distress. Logs will be checked daily. Any adverse event related to the training or blood collection will be immediately reported to the Principal and Co-Investigators.

DATA COLLECTION AND MANAGEMENT

We will obtain a certificate of confidentiality for this study. A participant's personal information could be linked with their study data. To minimize this risk, no one outside of the research team will have access to participants' data. Participants' data will only be identified in all computer analyses with their ID numbers. Any paperwork that includes participants' names or other personal information will be stored in a locked file cabinet in the locked lab. All data will be archived without personal identifiers, using only ID numbers. Emails to participants will be encrypted.

RECRUITMENT STRATEGY

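### Section 1.3 relies on observing participants for discomfort, but their video is off at all four training visits; separately, the 6.3 discomfort count names no source

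*Combined protocol and SAP*

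**What the plan says.** Section 1.3 notes that mindfulness practice may cause discomfort in people with earlier trauma or high current stress, and gives this safeguard: "Participants will be observed for any obvious discomfort and followed up with by the mindfulness teacher with trauma resources if necessary".

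Section 3.1 makes visits 2 to 5 virtual. Section 8.1 says of them: "During training visits, all videos (except the instructor's) will be turned off". Section 1.2 repeats the video-off rule for the Koru Mindfulness (KM) classes, with participants shown under an ID.

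Several other channels are planned:
- KM classes include shared reflection: "Each class will consist of an overview of 2-3 skills, group practice of the skills, and group reflection".
- Training visits in both arms have breakouts (4.2): "Breakout sessions for participants to share their thoughts and experiences in response to instructor's prompt".
- The synopsis adds regular check-ins by the teacher and weekly review by the Co-Investigators.
- Safety Management, which follows 8.1, says: "Daily practice logs will give participants a safe space to share any discomfort experienced during training" and "Logs will be checked daily".
- Section 5.4 gives the DASS-21 at the start of each visit and has the KM instructor read logs daily.

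Section 6.3 takes the number of participant reports of discomfort with a training procedure as a measure of safety. It names no form, question or schedule. Section 6.5 refers to journal entries and meditation logs when it sets out when an individual is stopped. KM reflections go into the Koru application. For the control arm, 4.2 says: "Participants in the CG intervention will be asked to journal by hand or via Qualtrics every day".

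**The concern.** There are two separate weaknesses.

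First, the safeguard that 1.3 attaches to its trauma-related risk cannot be carried out by sight in the classes where that risk arises. Section 4.4 requires withdrawal of KM participants in extreme discomfort, which presupposes that someone notices it.

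Second, the 6.3 count depends on participants choosing to mention discomfort somewhere. Without a fixed question, a low count could mean little discomfort or simply that nobody was asked. Section 2.1 says the pilot is to inform a larger study, so the count should be able to tell these apart.

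**Working it through.** The plan gives no figure to reproduce: 6.4 states that a power analysis does not apply. The check sets sections side by side, with simple counts for size.

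**1. Where observation by sight is possible.** The training visits are 2, 3, 4 and 5, all virtual (3.1), with participant video off (8.1; also 1.2 for KM). Sight is therefore available at 0 of 4 training visits. Visits 1 and 6 are in person, but no training takes place there.

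**2. Planned class exposure in the KM arm.** Inputs: 9 participants (3.2), 4 classes of 75 minutes (1.2).
- Participant-classes: 9 × 4 = 36.
- Minutes: 36 × 75 = 2,700.

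These are planned exposures, not missed events, and not every class minute is meditation. Home practice comes on top and was never open to observation.

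**3. What is left, and when it acts.**
- During class: reflection, breakouts and check-ins. All need the participant to say something, and the timing and content of the check-ins are not given.
- After class: log or journal entries, to be checked daily.
- Next visit: the DASS-21, which measures depression, anxiety and stress rather than discomfort with a procedure.

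**4. Delay to the next DASS-21.** Classes are weekly, so it comes about 7 days after visits 2, 3 and 4. For visit 5, section 3.3 puts visit 6 about 5 to 6 weeks after visit 1, or 35 to 42 days. Visits 2 to 5 span 3 × 7 = 21 days. That leaves 35 − 21 = 14 to 42 − 21 = 21 days for the two gaps at either end. If these are equal (my assumption), the gap from visit 5 to visit 6 is 14/2 = 7 to 21/2 = 10.5 days.

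**5. Source of the 6.3 count.**

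| Candidate source | Both arms? | Discomfort question stated? | Named in 6.3? |
|---|---|---|---|
| Logs and journals (6.5) | Yes, in different media | No | No |
| Same-day feedback survey (6.2) | Not restricted by arm | Items not shown | No |
| DASS-21 (5.4) | Yes | No; measures symptoms | Not as the source of the count |
| Teacher check-ins (synopsis) | Written about the Koru teacher | Concerns invited, no fixed question | No |

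Prompted answers designated as the source of the count: 0 at present. With one item after each class and full attendance: 18 × 4 = 72, or 36 per arm.

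**The case against.** The strongest reply on 1.3 is that being observed need not mean being seen. The classes are interactive, the teacher checks in, is trained in trauma-sensitive mindfulness and designed the visits with that in mind, psychiatric disease is excluded using the MINI, and KM participants in extreme discomfort are withdrawn and given resources. This stands to the extent that the classes are not unmonitored. A reader might infer that distress in class would go undetected or that safety is unmeasured; the documents do not support that. What remains is narrower: with video off, someone who stays silent gives the teacher no visible sign, so 1.3 describes a safeguard that does not work by sight.

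On 6.3, the same-day survey follows every training visit and is not limited to one arm. Its items are not shown, so it may already ask about discomfort. A reader might infer that no prompted source exists; the documents show only that 6.3 names none.

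A reader might also infer that control journals, which may be handwritten, are never collected. The synopsis and 6.1 both count submitted entries, 6.1 does so in each group, and Safety Management says logs are checked daily. The difference that stands is one of medium. It distorts no planned comparison, because no between-arm test of discomfort is planned.

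Finally, the incentives at 3 and 5 practice days a week (7.1) might suggest that logs miss much of the home practice. They do not show this: daily practice and logging are instructed, and a day without practice has no exposure to miss.

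**Conclusion.** Both parts hold in this limited form. Observation by sight is unavailable at all 4 training visits, covering 36 planned KM participant-classes. The 6.3 count names no source, and the records implied by 6.5 have no stated discomfort question and differ in medium by arm.

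The conclusion rests on taking observation in 1.3 in its ordinary visual sense and on the absence of any stated link between 6.3 and the feedback survey. If that survey already asks about discomfort, the second part shrinks to adding the link.

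Importance is low to moderate. The primary feasibility counts as planned are unaffected, and the DASS-21 remains a prompted safety measure in both arms, although it comes about a week later and does not ask about the training itself.

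**What to change.** - Add one fixed item on discomfort with that day's training (none / minimal / more than minimal) to the existing same-day feedback survey in 6.2. Use the same wording in both arms and attach the participant ID. If the survey already asks this, only link it to 6.3.
- Name this item in 6.3 as the source of the count. Report log and journal mentions separately; they also cover home practice.
- Send positive answers the same day to the Co-PI, who applies 6.5 as it stands. No change to the stopping rule is proposed.
- Reword 1.3 to name the check-ins, the logs and this item in place of observation.

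The cost is one survey item and wording in 1.3, 6.2 and 6.3, with no new visits or staff. There are three downsides. Prompted counts will run higher than spontaneous ones. An ID on the survey may make satisfaction answers less candid. And because 6.5, read literally, stops anyone who says the procedures contributed to discomfort of any degree, asking directly could raise withdrawals and so lower observed retention. The item gives prompted same-day detection; it does not restore live observation in class.

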1.4 Relevant Literature and Data

Our preliminary data, from a nationally representative US adult sample, found that a questionnaire measure of mindfulness moderates the relationship between alcohol misuse and self-report attention to reward (Figure 2). It is unknown whether increasing mindfulness will show similar effects using a task measure of attentional bias.

The Reward-Attentional Bias (Reward-AB) task will be used to measure attentional bias pre- and post-intervention. The task includes a training and testing portion, each of which are adapted from tasks described elsewhere that measure the influence of reward on visual attention [15, 20, 21].

Although not a primary objective, trait mindfulness will be measured using the Five Facet Mindfulness Questionnaire (FFMQ) and Mindful Attention Awareness Scale (MAAS). The FFMQ contains 5 subscales, with Cronbach alpha for the subscales ranging from 0.73 to 0.91 [22]. This measure has also been shown to reliably compare mindfulness pre- and post-training. The MAAS has been shown to have good 4-week test-retest reliability [23] and this measure correlates with other common measures of mindfulness, such as the Freiburg Mindfulness Inventory [24].

STUDY OBJECTIVES

The purpose of this pilot study is to explore the feasibility of the study design and compliance of freshman college students with task procedures.

2.1 Primary Objective

The primary objective will be to assess the feasibility of the study design and determine factors crucial to the success of a larger scale study, including those that influence recruitment and retention, consistency of practicing skills learned during training, and adherence to all study procedures.

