6.1 Primary Endpoint

1. Feasibility assessment [Time Frame: every week]
 - a. The feasibility of the study design will be measured using the total number of eligible participants, and retention rate for each visit, in addition to the one-month follow-up survey of enrolled participants. Compliance with individual training will be determined by the mean number of journal entries submitted per week in each group, due to previous evidence demonstrating an association between amount of homework completed and positive outcomes [40].

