6.3 Statistical Methods

The total number of eligible participants will be used as a measure of successful recruitment strategies and feasibility of enrollment criteria. The mean number of self-report training or journaling days recorded by participants and the total number of visits attended by each participant will be used as measures of compliance with study procedures. The number of times discomfort is reported by participants with any training procedure will be used as a measure of safety. A within-subjects ANOVA will be used to analyze the change in DASS-21 scores across the training visit weeks, including the total score and scores for all 3 subscales. A 1-Sided t-Test will be used to analyze the mean difference in CEQ score between the intervention and control group.

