7.1 Koru Mindfulness (KM) Intervention Group

Koru Mindfulness is a 4-week mindfulness meditation training initially designed for the emerging adult population (considered \leq 29 years). The skills are intended to help young adults manage stress, and thus can be advertised as an opportunity to learn skills in navigating college without having to mention mindfulness training anywhere in recruitment materials. The intervention will be delivered online through Zoom by a certified Koru instructor, with the goal of assessing the feasibility of an accessible intervention for college students. Koru is delivered with a mix of PowerPoint slides, group training of mindfulness and meditation skills and discussion, and daily logging of practice with an application or journal. The training is accompanied by the book *The Mindful Twenty-Something* [44].

Participants will be encouraged to practice daily any of the mindfulness and meditation skills that were previously learned. To incentivize compliance with training, monetary incentives will be given to individuals who practice ≥ 3 days/week and those who practice ≥ 5 days/week.

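### Consistency of practice is part of the primary objective, but practice is summarised only by group means or totals, which at low and middle levels cannot show how many participants keep practising

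*Combined protocol and SAP*

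**What the plan says.** Section 2.1 includes "consistency of practicing skills learned during training, and adherence to all study procedures" among the matters that the primary objective is to settle for a larger study.

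Practice is then summarised in four places:

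- Section 6.1 (primary endpoint, assessed weekly): "mean number of journal entries submitted per week in each group".
- Section 6.3: "The mean number of self-report training or journaling days recorded by participants".
- Synopsis, statistical plan: "the secondary outcome will be measured by total journal entries submitted during the 4 weeks of intervention training".
- Synopsis, efficacy evaluations: "Mean number of visits attended by participants and total number of journal entries".

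Section 6.3 has one compliance measure defined for the individual, "the total number of visits attended by each participant", and 6.1 has retention at each visit. Both concern attendance. No standard deviation, distribution, within-person weekly pattern or proportion reaching a level of practice is planned.

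A weekly level for the individual does appear in section 7.1 on the mindfulness arm, where money is paid to "individuals who practice ≥ 3 days/week and those who practice ≥ 5 days/week". It serves as a payment rule and is not carried into the endpoint.

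**The concern.** Consistency is a property of a person followed over weeks. A group mean or total measures volume, and the same volume can come from a class that all practise steadily or from a smaller number who practise more while others have stopped. Attendance does not fill the gap, because a participant can come to every class and do no practice between classes.

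The stake is the use of the pilot. With no power analysis (6.4), its descriptive summaries are its main product. Section 6.1 justifies counting entries by citing published evidence that the amount of homework done goes with better outcomes. A mean of 3 days produced by nine people and the same mean produced by five call for different planning of the larger trial.

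**Working it through.** The plan states no practice rate or target, so there is no figure of its own to reproduce. The check asks whether two different classes can agree on every planned practice summary.

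**Inputs.** 9 participants per arm (3.2); 4 training weeks (1.2, 4.2); daily practice or journalling requested, so at most 7 practice days a week (4.2); levels of 3 and 5 days a week (7.1, mindfulness arm). Assumption: one entry per day, so that entries and days coincide. The two classes are illustrations; the documents give no distribution of practice.

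| Summary | Class 1: all steady | Class 2: four stop after week 1 |
|---|---|---|
| Days in week 1 | 9 × 3 = 27 | 9 × 3 = 27 |
| Days in each of weeks 2 to 4 | 9 × 3 = 27 | 5 + 5 + 5 + 6 + 6 + 4 × 0 = 27 |
| Four-week total | 4 × 27 = 108 | 4 × 27 = 108 |
| Group mean, every week | 27/9 = 3.0 | 27/9 = 3.0 |
| Mean days per participant | 108/9 = 12.0 | 108/9 = 12.0 |
| *Not planned:* at least 3 days in all 4 weeks | 9/9 | 5/9 |
| *Not planned:* at least 5 days, each of weeks 2 to 4 | 0/9 | 5/9 |
| *Not planned:* no practice in week 4 | 0/9 | 4/9 |
| *Not planned:* SD of participant totals | 0 | 8.6 |

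The SD in class 2 comes from totals of 18 (three people), 21 (two) and 3 (four) about a mean of 12: √[(3 × 36 + 2 × 81 + 4 × 81)/8] = √(594/8) = 8.6.

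**Exact (Clopper-Pearson) 95% intervals.** For x of n, the limits are the 0.025 quantile of Beta(x, n − x + 1) and the 0.975 quantile of Beta(x + 1, n − x). For 9/9 the lower limit is 0.025^(1/9) = 0.664, giving 66-100%. For 5/9 the limits are 0.212 and 0.863, giving 21-86%.

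**Where the ambiguity ends.** If k of 9 are inactive in a week, the group mean of days cannot exceed 7(9 − k)/9:

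- k = 1: 6.22
- k = 2: 5.44
- k = 3: 4.67
- k = 4: 35/9 = 3.89
- k = 5: 3.11

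A weekly mean above 3.89 therefore excludes four inactive, although at 4.0 three can still be silent: 5 × 7 + 1 + 3 × 0 = 36 = 9 × 4.

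**What a weekly mean does show.** If four stop and the other five stay at 3 days, the mean falls from 3.0 to 5 × 3/9 = 1.67, and the drop is visible. Its source is not: six people at 2 days and three at 1 day also give 6 × 2 + 3 × 1 = 15 days and 1.67. In the first case 5/9 reach 3 days and in the second 0/9 do.

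**The case against.** The strongest points on the other side are these.

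- **The weekly mean is a partial answer.** Section 6.1 is assessed every week, so a decline shared by the class would show. This stands. A reader might infer that the consistency part of the objective goes wholly unanswered; the documents do not support that. What is missing is the number of people behind the mean. The exact match in class 2 also needs the remaining five to practise more as the four stop.
- **The ambiguity is bounded.** A reader might infer that nearly half a class could stop unseen at any level of practice. The 3.89 ceiling rules that out for higher means.
- **Section 2.1 can be read as asking for factors that influence consistency.** This is a fair reading, and the added table identifies no factors by itself. But factors can be related to consistency only if it is measured per participant. Section 5.1 collects questionnaires to look at individual differences, and there is no planned practice value per person to set beside them.
- **No evidence that practice will be uneven.** Correct: the documents give no distribution. The point rests on what the summaries can distinguish, not on a prediction.
- **This is an 18-person pilot with no practice threshold for success, and individual logs will exist.** True, so nothing is invalidated and individual values could be reported anyway. The plan does not commit to doing so.
- **The 3- and 5-day levels are payment triggers, stated only for the mindfulness arm.** This stands and limits any comparison between arms.

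**Conclusion.** The concern holds, within limits. One named part of the primary objective has no planned summary that shows how many participants keep practising. Two classes of nine can agree on the total (108 days), the mean in every week (3.0) and the mean days per participant (12.0), yet differ as 9/9 against 5/9 in those who reach 3 days in all four weeks.

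This rests on 9 per arm, at most one counted entry per day, and illustrative patterns. If several entries a day are accepted, the 3.89 ceiling still applies to days but no longer to entries. The plan also does not say whether leavers stay in the denominator; dropping them would make the mean look better.

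The intervals of 66-100% and 21-86% overlap. A reader might take the added proportions as a way to test one arm against the other, but at this size they only describe. This is a change worth making before analysis, not a flaw that undermines the pilot.

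**What to change.** In sections 6.1 and 6.3, keep the mean as a descriptive line and define consistency per participant from distinct calendar days with a log. Add:

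- for each arm and each of the 4 weeks, the number and proportion of all randomised participants who logged on at least 3 days and on at least 5 days;
- for each arm, the number who reached at least 3 days in all 4 weeks;
- a rule that participants who have left count as not meeting the level;
- exact 95% confidence intervals, stated to be descriptive and not a between-arm test.

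Both levels are needed: in the example, class 1 leads at 3 days and class 2 leads at 5 days in weeks 2 to 4.

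**Cost.** New wording and one small table. For the mindfulness arm the per-person weekly counts are already needed to pay the incentive. For the control arm, journals may be kept by hand or in Qualtrics (4.2), and the plan does not say that paper entries are dated or how they are gathered, so a dating instruction and a collection step are needed.

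**Downside.** The payment levels are described for the mindfulness arm and not in the control-arm section. The plan should say so beside the table, and state that any difference between arms may reflect the incentive.
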